Geometrical Facial Deformation According to Posture and Non-invasive Ventilation Mask Virtual Fit in Amyotrophic Lateral Sclerosis

Background

Amyotrophic lateral sclerosis (ALS) is a progressive neurodegenerative disease that eventually affects the respiratory muscles. In most cases of the slow progression of respiratory failure, noninvasive ventilation (NIV) is the first treatment option. NIV treatment provides a better quality of life and is, therefore, strongly recommended; however, its use must consider the type of ALS. Severe bulbar dysfunction limits NIV treatment. Aside from additional NIV options in ALS, including mouthpiece ventilation and intermittent abdominal pressure ventilation, prolonged use of a ready-made face mask is impractical for several reasons. Cognitive impairments can affect the maintenance of NIV. Hypersalivation and bronchial secretion disrupting ventilation can lead to poor NIV adherence. Pressure injuries are another clinical issue. The incidence of pressure injuries associated with NIV masks ranges from 10–31%. Long-term use of NIV face masks can result in pressure injuries at the contact area, and skin-protective patches may not prevent skin problems. Patients with bulbar ALS frequently have postural facial deformations, and these can lead to difficulties in wearing the NIV mask. No previous study has analyzed morphological differences in facial soft tissue according to posture in ALS.

Objective

The aim of this study was to compare the deformations of the face in different postures in subjects with bulbar ALS and healthy participants. This study also virtually fitted an NIV mask to understand how the NIV mask interface affects the face in different postures.

Methods

Participants

	Amyotrophic lateral sclerosis with bulbar involvement patients	Healthy participants
Inclusion criteria	
 • a patient with Amyotrophic Lateral Sclerosis, 16-60 years old • a patient with respiratory difficulty • a patient who requires or anticipates mechanical ventilation 	
 • a volunteer without history of facial surgery or neuromuscular disease, 16-60 years old • a volunteer without respiratory difficulty

	
 • a patient who visit out- or inpatient clinic at rehabilitation hospital 	
Exclusion criteria	
 • a patient who cannot scan due to respiratory instability • a patient who cannot bear posture for 3D scanning 	
 • a volunteer with neuromuscular disease • a volunteer with history of facial surgery or palsy

Interventions

The face is scanned with 5-camera unit 3D scanning system (3dMD, Atlanta, Georgia) in the sitting, supine, and lateral decubitus positions. Ten anatomical landmarks are located in the nasal root area for 4 points (sellion, glabella, left dacryon, and right dacryon) and in the oral area for 6 points (subnasale, SN; labial superius, LS; labial inferius, LI; cheilion left, CL; cheilion right, CR; and promentale, PM) where major skin deformations occur. Each subject should keep their mouth closed naturally during scanning. The amounts of change of a landmark position in the anteroposterior or lateral direction according to the posture change (from sitting to supine; from sitting to lateral decubitus) are measured.

Outcome measurements and statistical analysis

Primary outcome measure: The change in position of anatomical landmarks

Change is reported as the mean displacement (mm) during the change in position from the initial position (sitting) to the subsequent position (supine & side-lying). The extent of facial landmark changes in different postures indicative of facial deformation in healthy subjects and subjects with bulbar ALS will be compared. A repeated-measures analysis of variance will be performed at a $\alpha = 0.05$ to assess the effectiveness of the group and posture. The Tukey-Kramer method will be used as a post hoc analysis for multiple comparisons of means at a $\alpha = 0.05$. All analyses will be performed using Minitab v.19 (Minitab, State College, Pennsylvania).

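### Does the virtual mask fit need its own outcome definition and placement rule in the plan?

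*Combined protocol and SAP*

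**What the plan says.** The title of the combined protocol and SAP includes the words "Non-invasive Ventilation Mask Virtual Fit in Amyotrophic Lateral Sclerosis". The Objective has two sentences. The first compares facial deformation across postures between bulbar ALS and healthy participants. The second is "This study also virtually fitted an NIV mask to understand how the NIV mask interface affects the face in different postures".

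The Background supplies the clinical reason: "Long-term use of NIV face masks can result in pressure injuries at the contact area".

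Under Interventions, the scans are taken "in the sitting, supine, and lateral decubitus positions". Ten landmarks, four at the nasal root and six around the mouth, are placed "where major skin deformations occur". Landmark shifts are measured front-to-back or sideways, from sitting to each of the other two postures.

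Under Outcome measurements and statistical analysis, one outcome is defined: "Primary outcome measure: The change in position of anatomical landmarks". It is summarised as a mean displacement in mm and analysed by repeated-measures ANOVA on group and posture, with Tukey-Kramer comparisons. The section ends with "All analyses will be performed using Minitab v.19", which names software and adds no further outcome.

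**The concern.** One of the two stated aims, and part of the title, has no outcome attached. Landmark displacement cannot stand in for it: that compares a face with itself across postures, whereas a mask fit needs a distance between mask and skin.

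The missing item with the most leverage is the placement rule. The same scans could show a gap at the nasal root if the mask is held in its sitting pose, and an overlap there if it is re-seated on the mouth. Since the study is motivated by pressure injury where the mask touches the skin, gap against overlap is the substance of this aim. If the rule were chosen after fits had been seen, a reader could not tell from the plan.

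**Working it through.** **Text check.** Occurrences of mask: title 1, Background 4, Objective 2, Methods 0 (1 + 4 + 2 = 7). Nothing suggests that blacked-out text or a missing figure accounts for this. Mask model, placement rule, fit measure and summary are all absent. The plan states no figure for the fit, so there is nothing to reproduce.

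**Can placement change the result?** The documents give no displacements, so all shifts here are assumptions. Let a be the nasal root shift and b the oral shift, in mm, positive when skin moves away from the mask. The mask touches both areas in the sitting scan. It is rigid and moves a distance t along one axis without tilting. Clearance is shift minus mask movement: nasal = a − t, oral = b − t. Positive is a gap, negative an overlap. Take a = 1 and b = 3.

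| Placement | t | Nasal | Oral |
|---|---|---|---|
| Sitting pose kept | 0 | 1 − 0 = +1 | 3 − 0 = +3 |
| Re-seated on nasal root | 1 | 1 − 1 = 0 | 3 − 1 = +2 |
| Equal-weight best fit | (1 + 3)/2 = 2 | 1 − 2 = −1 | 3 − 2 = +1 |
| Re-seated on oral area | 3 | 1 − 3 = −2 | 3 − 3 = 0 |

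For other assumed pairs, the nasal range over these four placements is −0.5 to +0.5 mm (a = 0.5, b = 1) and −3 to +2 mm (a = 2, b = 5).

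Weighting by all ten landmarks gives the same picture for a = 1, b = 3. Mean clearance is (4 × 1 + 6 × 3)/10 = +2.2 mm with the sitting pose kept, and (4 × (−2) + 6 × 0)/10 = −0.8 mm when re-seated on the oral area. This uses the same no-tilt assumption, so it does not test that assumption.

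**How far does that carry?** The gap-to-overlap change depends on the model:

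- *Tilt allowed.* The two areas can be matched separately, with movement 1 at the nasal root and 3 at the mouth: nasal 1 − 1 = 0, oral 3 − 3 = 0. Re-seating produces no overlap. A real mask contour has more than two contact points, so some residual would remain, but its sign no longer follows from the table.
- *Equal shifts.* For a = b = 1, clearance is +1 if kept and 0 if re-seated. The size changes and no overlap appears.
- *Shifts toward the mask.* For a = −1, b = −3, the kept pose gives nasal −1 (overlap) and oral re-seating gives −1 + 3 = +2 (gap), the reverse of the table.
- *Opposite shifts.* For a = −1, b = 2, nasal clearance runs from −3 to 0. There is no gap under any of the four placements.
- *Sideways movement.* The plan also measures lateral shift and includes side-lying. One axis toward or away from the mask does not represent that posture change.

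**What else depends on placement?** The primary outcome is computed from landmark coordinates with no mask in the formula, so t does not enter it. The scans in three postures serve any placement chosen later, including more than one.

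**The case for a change.** The strongest case for a change is that the fit is a title element and a stated aim, and the plan nowhere calls it illustrative. Even a descriptive result needs a mask, a placement and a unit before anyone can reproduce it. A few lines of wording would supply these, with no extra visits or scans.

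Part of this stands. The absence is a matter of record, and the plan alone does not show that the placement was fixed in advance.

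Two supporting arguments do not stand. First, one can construct a nasal difference between groups that is 0 under one placement and 1 to 3 mm under another, by assuming that the groups differ only in oral shift by 1 to 3 mm. But the mask sentence refers to postures, not groups. The ALS-healthy comparison belongs to the first aim and its landmark outcome. Second, the past tense of the mask sentence might suggest that fits had already been seen. The first aim is also in the past tense while its analysis is in the future tense, so tense does not set the mask fit apart.

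What remains is a request to write down choices. Leaving the mask in place and re-seating it each answer a reasonable question, so choosing one in the text would not correct an error.

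**Conclusion.** This is a gap in the written detail that the analysts have to fill in order to do the work, and it calls for no change to the plan. A virtual fit cannot be produced without selecting a mask, positioning it and measuring something. Those choices can be reported with the result.

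No stated rule is wrong. No significance test, error rate or outcome is tied to the fit. The effect on the primary landmark comparison is zero, and no data are lost.

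The possible effect on the fit itself cannot be sized from the documents. The swing from a 1 mm gap to a 2 mm overlap rests on assumed shifts of 1 and 3 mm away from a rigid mask that moves along one axis without tilting. It does not appear with equal shifts, with shifts in opposite directions, or with a mask that can tilt onto both areas. The conclusion assumes that the fit is reported as a description by posture. That is a reading of the Objective, because the plan does not say so outright.

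### Do the ALS inclusion criteria let non-bulbar patients into a study about bulbar ALS?

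*Combined protocol and SAP*

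**What the plan says.** All the relevant text is in one short document.

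- **Background.** The expected effect is tied to bulbar disease: "Patients with bulbar ALS frequently have postural facial deformations, and these can lead to difficulties in wearing the NIV mask".
- **Objective.** The aim is to "compare the deformations of the face in different postures in subjects with bulbar ALS and healthy participants".
- **Methods, Participants, column heading.** The patient column is headed "Amyotrophic lateral sclerosis with bulbar involvement patients".
- **Methods, Participants, inclusion bullets.** There are four: "a patient with Amyotrophic Lateral Sclerosis, 16-60 years old"; "a patient with respiratory difficulty"; "a patient who requires or anticipates mechanical ventilation"; and "a patient who visit out- or inpatient clinic at rehabilitation hospital".
- **Methods, Participants, exclusion bullets.** One is "a patient who cannot scan due to respiratory instability"; the other concerns inability to hold the scanning posture.
- **Outcome measurements and statistical analysis.** The comparison is again described as one between healthy subjects and subjects with bulbar ALS, by repeated-measures ANOVA at a 0.05 level with Tukey-Kramer comparisons.

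The title speaks of ALS without the bulbar qualifier. Nowhere is bulbar involvement defined by a sign, scale, threshold or assessor.

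**The concern.** A screener who works from bullets alone would check diagnosis, age, breathing, expected need for ventilation and clinic attendance. A patient whose ALS affects the respiratory muscles but spares bulbar function passes all of these, and neither exclusion stops entry. The bullets select on breathing, whereas the hypothesis is about bulbar disease, and six of the ten landmarks lie in the oral area.

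If such patients were enrolled and their faces deformed less with posture, two things would follow. The ALS-versus-healthy difference would shrink and its variance would grow, so a real effect could be missed. The conclusion would also be worded for a population that the sample did not represent. Because the plan names no measure of bulbar severity, the mixing would be hard to see afterwards.

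**Working it through.** **Step 1: does the text admit non-bulbar patients?**

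| Place | Population named |
|---|---|
| Title | ALS |
| Objective | bulbar ALS |
| Eligibility table, column heading | ALS with bulbar involvement |
| Eligibility table, four inclusion bullets | ALS; bulbar status not mentioned |
| Eligibility table, two exclusion bullets | bulbar status not mentioned |
| Analysis text | bulbar ALS |

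The three places that define the group being compared agree, and one of them is inside the eligibility table. In a two-column table the heading names the population and the bullets narrow it. No bullet says that bulbar involvement is unnecessary. So non-bulbar patients qualify only if staff apply the bullets and ignore the heading above them.

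**Step 2: what would dilution cost if the heading were ignored?**

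The documents give no sample size, effect size, standard deviation or power, so there is no planned figure to reproduce. The following is illustration only. Assumed inputs: *n* per group; a true bulbar-versus-healthy difference of *d* = 1 SD; a share *q* of the ALS group that is non-bulbar and behaves exactly like healthy volunteers; and a two-sided two-sample t-test. Only the 0.05 level comes from the plan, which does not state sidedness.

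- Observed difference: *d*(1 − *q*)
- ALS-group variance: 1 + *q*(1 − *q*)*d*²
- Noncentrality: *d*(1 − *q*) / √{[1 + 1 + *q*(1 − *q*)*d*²] / *n*}, with 2*n* − 2 degrees of freedom

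For *n* = 15 and *q* = 0.2, the difference is 0.8, the variance is 1 + 0.2 × 0.8 = 1.16, and the noncentrality is 0.8 / √(2.16/15) = 2.108. Power is then 0.530.

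| Non-bulbar share *q* | *n* = 15 | *n* = 25 | *n* = 30 | *n* = 60 |
|---|---|---|---|---|
| 0 | 0.753 | 0.934 | 0.968 | >0.99 |
| 0.05 | 0.699 | 0.902 | 0.947 | >0.99 |
| 0.2 | 0.530 | 0.760 | 0.834 | 0.987 |
| 0.3 | 0.421 | 0.636 | 0.718 | 0.951 |
| 0.5 | 0.239 | 0.372 | 0.435 | 0.726 |

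**Step 3: how firm are these figures?**

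Zero effect in non-bulbar patients is the worst case, short of deformation in the opposite direction. The Background says deformation is frequent in bulbar ALS; it does not say that it is absent in other ALS. If non-bulbar patients showed half the effect, then at *n* = 15 and *q* = 0.2 the difference would be 0.8 × 1 + 0.2 × 0.5 = 0.9, the variance 1 + 0.16 × 0.25 = 1.04, the noncentrality 0.9 / √(2.04/15) = 2.44, and power 0.654 in place of 0.530.

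A single-endpoint t-test is also not the planned analysis, which is a repeated-measures ANOVA of group and posture. The direction of the effect is credible, but the size cannot be fixed from the documents. When the heading is applied, *q* = 0 and the top row holds.

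**The case for a change.** The strongest reply is that a heading shows intent but cannot be audited. The healthy column makes the contrast: its bullets spell out what healthy means (no facial surgery, no neuromuscular disease, no respiratory difficulty), while the ALS column leaves its defining feature undefined. Two screeners could judge a mild or early bulbar case differently, and a reader could not check afterwards who was included. An added line would cost almost nothing.

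Much of this stands as a matter of documentation. Bulbar involvement is indeed not operationalised, and a stated criterion would make the table tidier. It does not show that the plan would go wrong if followed. Disagreement over borderline cases is a different and smaller matter than admitting patients with no bulbar involvement, and it is the latter that the dilution argument needs. Nothing in the documents suggests that non-bulbar patients were meant to enter, or that a share of 20% to 50% is likely.

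**Conclusion.** No change to the plan is called for. The column heading, the objective and the analysis text all name bulbar ALS; the bullets leave it unrepeated but do not contradict it. A team that follows the table, heading included, enrols the intended group, and the conclusion then matches the sample.

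The dilution is conditional on the heading being disregarded. In that case the loss could run from small (0.753 to 0.699 with 15 per group and 5% non-bulbar) to severe (0.753 to 0.239 at 50%), but these figures rest on an assumed group size, effect size and non-bulbar share, and on the assumption that non-bulbar patients have no effect. With the heading applied, the share is zero and so is the loss.

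The remaining gap is the missing definition of bulbar involvement. This assumes that recruiting clinicians can recognise bulbar involvement from ordinary clinical assessment, which is reasonable for patients drawn from a rehabilitation hospital and already needing or expecting ventilation.

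### Earlier facial surgery or palsy bars healthy volunteers but not ALS patients, so facial mobility altered by causes other than ALS can enter only the ALS group

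*Combined protocol and SAP*

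**What the plan says.** Eligibility is set out in a two-column table under Methods, Participants. In the healthy column, facial surgery appears twice. The inclusion list asks for "a volunteer without history of facial surgery or neuromuscular disease, 16-60 years old", and the exclusion list removes "a volunteer with history of facial surgery or palsy".

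The ALS column opens with "a patient with Amyotrophic Lateral Sclerosis, 16-60 years old" and goes on to respiratory difficulty, current or expected need for ventilation, and attendance at the rehabilitation hospital. It has two exclusions: "a patient who cannot scan due to respiratory instability" and "a patient who cannot bear posture for 3D scanning". Neither list in that column mentions facial surgery or palsy.

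The Interventions section places ten landmarks, four around the nasal root and six around the mouth, at sites "where major skin deformations occur". The primary outcome is each landmark's displacement in mm from the sitting position. On the comparison, the outcome section says: "The extent of facial landmark changes in different postures indicative of facial deformation in healthy subjects and subjects with bulbar ALS will be compared". The analysis is a repeated-measures ANOVA on group and posture, with Tukey-Kramer comparisons afterwards.

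**The concern.** The study exists to contrast bulbar ALS with healthy faces, and the group term carries that contrast. A characteristic that can alter postural movement of facial soft tissue, and that is allowed in one group and barred from the other, becomes part of the group term.

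Earlier surgery to the nose, lips or jaw, or residual palsy from a cause other than ALS, could be such a characteristic, because it may change how the tissue at these landmarks moves. Lax, palsied tissue might move more and make the ALS effect look larger. Scar tethering or an implant might restrict movement and make it look smaller. In either case the difference would be attributed to ALS although part of it had another cause.

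**Working it through.** The documents give no figure to reproduce: they state no sample size, SD, expected displacement or prevalence of facial surgery or palsy. The check is mainly a comparison of the criteria, followed by illustrative arithmetic on assumed inputs.

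**1. The two columns side by side**

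| History | Healthy volunteers | ALS patients |
|---|---|---|
| Facial surgery | Barred by inclusion and by exclusion | Not mentioned |
| Facial palsy, cause other than ALS | Barred by exclusion | Not mentioned |
| Facial weakness due to ALS | Does not arise (neuromuscular disease barred) | Part of the condition studied |

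The third row differs by design. The first two differ without a stated reason.

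**2. Does anything later in the plan close the gap?** The analysis names group and posture as its factors. No covariate for facial history, no collection of that history in ALS patients, and no sensitivity analysis is described.

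**3. Which facial histories can matter?** The outcome is a within-person change: position in the new posture minus position when sitting. A feature that is the same in every posture subtracts out. What remains is a difference in how far the tissue moves, and only at the ten nasal-root and oral landmarks. Surgery elsewhere on the face, or old surgery that left normal mobility, need not contribute.

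**4. Size, by assumption only.** Let f be the share of ALS patients affected and d their mean shift in displacement relative to other ALS patients. Because f is zero by rule among the volunteers,

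shift in group difference = f × d

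- f = 0: shift = 0, whatever d is
- f = 0.05, d = 0.5 SD: 0.05 × 0.5 = 0.025 SD
- f = 0.20, d = 1.0 SD: 0.20 × 1.0 = 0.20 SD

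For a single affected patient in a group of n, f = 1/n and the shift is d/n. With d assumed to be 1 to 3 mm:

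- n = 10: 1/10 to 3/10 = 0.10 to 0.30 mm
- n = 20: 1/20 to 3/20 = 0.05 to 0.15 mm

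The values of f, d and n are all assumptions. The sign of d may be positive or negative.

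**The case against.** The strongest reply is that most of the asymmetry is harmless or intended. Facial weakness may be part of bulbar disease, so a palsy exclusion for volunteers and none for patients is what one would expect. Change from sitting removes any static feature. The healthy criteria may simply define a normal reference group, since the same column also bars neuromuscular disease and respiratory difficulty. A broad ALS sample also suits the second aim, virtual mask fitting, and a blanket surgery exclusion would remove patients with trivial procedures from a group that may be hard to recruit.

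Much of this stands, and it limits the point. A reader might infer that any scarred, implanted or palsied face in the ALS group would be read as ALS deformation. The documents do not support that, because the outcome is a change within each person and only altered mobility at the landmarks survives the subtraction. A reader might also infer that the sponsor has acknowledged surgery and palsy as disturbing the endpoint. The plan gives no reason for the criteria, so that is a guess. Nor do the documents show that bias of any given size will occur.

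What does not stand is the idea that these arguments justify a one-sided rule on surgery or on palsy from other causes. Neither is part of ALS. Wanting a representative sample for mask fitting could support relaxing the rule in both groups; it does not explain applying it to volunteers only when the primary contrast is meant to isolate ALS.

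**Conclusion.** The point holds in a limited form. The gap in the criteria is explicit, and nothing later in the plan closes it. Followed as written, the plan lets landmark mobility altered by earlier surgery or a non-ALS palsy into the ALS group only, and the group term absorbs any effect.

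Confidence is high for the asymmetry and low for its consequence. The bias is zero if no such patient enrolls, its direction is not fixed, and its size cannot be judged from the documents. The illustrative shifts show only that one affected patient in a small group could move the mean by a few tenths of a millimeter at most under the assumed inputs; the plan gives no expected group difference to set this against. The point is a correctable weakness in the comparability of the groups on the primary outcome, not evidence that the comparison is invalid.

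**What to change.** Add a counterpart to the ALS exclusion list: a history of facial surgery involving the nasal or oral landmark regions, or facial palsy documented as not attributable to ALS. Limiting surgery to those regions avoids losing patients over irrelevant procedures. Asking for documentation of the cause of a palsy keeps ALS-related weakness in the sample and avoids having to separate old palsy from bulbar weakness at the scan.

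The Objective is partly in the past tense and the analysis in the future tense, so enrollment may already have taken place. In that case, or if exclusion is impractical, record the same history for every ALS patient and prespecify a sensitivity analysis that repeats the primary repeated-measures ANOVA without those affected. Report how many there were.

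The cost is one eligibility line and one history item, plus one repeated analysis under the fallback. The small downside is the possible loss of a few ALS candidates.

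### The ALS-versus-healthy comparison has no safeguard against an age or sex imbalance: no matching is described and the ANOVA names only group and posture

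*Combined protocol and SAP*

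**What the plan says.** The Objective is to "compare the deformations of the face in different postures in subjects with bulbar ALS and healthy participants". Under Methods, Participants, the patient column admits "a patient with Amyotrophic Lateral Sclerosis, 16-60 years old", and patients are drawn from the clinic of a rehabilitation hospital. The healthy column admits "a volunteer without history of facial surgery or neuromuscular disease, 16-60 years old". No matching or balancing of the two groups is described, and sex appears nowhere in the document.

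Under Interventions, landmark movements "according to the posture change (from sitting to supine; from sitting to lateral decubitus) are measured". Each person therefore has two posture changes, both taken from their own sitting scan.

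Under Outcome measurements and statistical analysis: "The extent of facial landmark changes in different postures indicative of facial deformation in healthy subjects and subjects with bulbar ALS will be compared". The model is a repeated-measures ANOVA at alpha 0.05 "to assess the effectiveness of the group and posture". Of the follow-up it says: "The Tukey-Kramer method will be used as a post hoc analysis for multiple comparisons of means". No covariate, adjusted model, baseline table or sensitivity analysis for imbalance is specified.

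**The concern.** The only stated outcome is meant to be read as facial deformation due to bulbar ALS. With clinic patients on one side and volunteers on the other, age and sex are the most basic rival explanations for a group difference, and the plan neither balances them by design nor adjusts for them in the analysis.

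Two features of the plan look protective but are only partly so. Measuring change from each person's own sitting scan removes fixed differences in face shape. It does not remove an effect of age or sex on the amount of movement, which is the outcome itself. The common age window bounds age but does not balance it. Tukey-Kramer controls multiplicity, not confounding.

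If an imbalance did occur and did matter, part of the reported ALS effect could be an age or sex effect, or a real difference could be masked. A chance imbalance shrinks as the sample grows. A systematic one, for example from where volunteers are found, does not.

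**Working it through.** **Inputs from the documents.** Age limits 16 and 60 in both groups; alpha 0.05; two posture changes per person. No sample size, standard deviation, effect size, or age or sex distribution is given, so there is no figure in the plan to reproduce. Everything numerical from here on is assumed, and refers to one landmark in one direction.

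**1. Does the window prevent a gap?** It spans 60 - 16 = 44 years. With assumed truncated-normal ages inside it, group means of 47 and 38 differ by 9 years (1.1 SD), and means of 49 and 31 by 18 years (2.6 SD). Gaps of 1 to 2 SD are therefore possible, though nothing says that they will occur.

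**2. Which results are biased?** Write the displacement of a person at posture change j as m_j + d_j × group + b_j × age + error, where d_j is the disease effect and b_j the age effect. Let G be the age gap between groups. Without adjustment:

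- the group difference at posture change j estimates d_j + b_j × G;
- the group difference averaged over both changes estimates the mean of the d_j plus G × (b_supine + b_lateral)/2;
- the group-by-posture interaction estimates (d_supine - d_lateral) + G × (b_supine - b_lateral).

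The first is biased whenever age acts at that posture. The third is biased only if the age effect differs between the two posture changes. The same algebra holds for sex.

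**3. Size for one posture change.** The bias is age correlation × gap, in SD units. For 15 per group the noncentrality is bias × √(15/2), with 28 degrees of freedom and critical t 2.048. At correlation 0.3 and a 1-SD gap, the bias is 0.3 × 1 = 0.3 SD and the noncentrality is 0.3 × 2.74 = 0.82. The rejection rate is then 0.125; simulation gives 0.127. With age and sex adjusted it is about 0.05.

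| Bias (SD) | 10 per group | 15 per group | 30 per group |
|---|---|---|---|
| 0.1 | 0.055 | 0.058 | 0.067 |
| 0.3 | 0.097 | 0.125 | 0.208 |
| 0.6 | 0.246 | 0.355 | 0.628 |

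The table also applies to the posture-averaged group effect if the bias is expressed in SDs of a person's mean displacement. For sex, an assumed 0.5-SD effect and a 40-point difference in sex mix give 0.5 × 0.40 = 0.2 SD, and a rate of 0.083 at 15 per group.

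**4. Size for the interaction.** Simulation with 15 per group, supine age correlation 0.3, between-posture correlation 0.5 and a 1-SD gap:

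- no age effect in lateral decubitus: 0.123;
- half the supine effect: 0.066;
- the same effect: 0.05.

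Only the first, extreme case shows clear inflation (0.337 at a 2-SD gap). Adjustment by posture brings it to about 0.05.

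**5. Is a main-effect covariate enough?** No. Age is constant within a person, so a main effect cancels out of supine minus lateral. On one test data set the interaction F was 1.296 both without age and with age as a main effect, and 0.262 with age-by-posture. In the supine-only case at a 1-SD gap, the supine bias is 0.30 SD unadjusted. With main effects alone it is 0.15 SD, with -0.15 SD introduced in lateral decubitus. With covariate-by-posture terms it is 0.00.

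**The case against.** The strongest reply is that both premises are unsupported. Nothing in the documents says that age or sex changes postural displacement, or that the groups will differ on either, and both must hold for any bias to arise. At the low end, a bias of 0.1 SD gives about 6%, which is effectively no problem. The shared age limits and the change-from-sitting measure already remove part of the risk. This is also a descriptive comparison with no treatment claim, so a full covariate-by-posture model as the main analysis may be more than it needs.

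Much of this stands. It makes the harm conditional and the magnitudes illustrative, and it argues for a simple adjusted comparison beside the planned one instead of a replacement. It does not supply a safeguard that the plan lacks.

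It is also true that adjustment is weakest where the possible bias is largest, because a wide age gap leaves little overlap between groups. That favours balanced recruitment where it is still possible.

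A reader might go further and infer that the group-by-posture interaction is confounded by any age or sex imbalance. It is not: with an equal effect at both posture changes it stays at about 5%. Nor does the plan explicitly name an interaction term. The overall posture effect is a within-person contrast and is not part of this concern.

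**Conclusion.** The point holds as a gap in the plan that is cheap to close, not as a demonstrated bias. Group is non-randomised, no age or sex balancing is described beyond the 44-year window, and the named model contains neither variable. The posture-averaged group difference and the group difference at each affected posture are therefore open to confounding.

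The illustrative 12-13% against 5% rests on 15 per group, an age correlation of 0.3 and a 1-SD gap, all assumed. Other plausible inputs run from near nominal to several times nominal. A reader might conclude that the planned result will be wrong, or that the groups are imbalanced. The documents support neither, since they give no age or sex distribution and no evidence that either variable affects displacement.

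**What to change.** In Outcome measurements and statistical analysis, add a group comparison adjusted for age (continuous) and sex for each posture change. Equivalently, put age and sex with their posture interactions into the repeated-measures model. Report adjusted and unadjusted group differences side by side, and tabulate age and sex by group. The table shows an imbalance but does not remove it, so it should not stand alone.

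If recruitment is still open, recruit volunteers to a similar age and sex mix as the patients. The Objective is written in the past tense and the analysis in the future tense, so the recruitment status is unclear.

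The cost is one recorded item (sex; age is already needed for eligibility), a few lines of text and a little analysis. In power, for an assumed true 1-SD supine difference and 15 per group:

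- **Exact balance:** two error degrees of freedom are lost (28 to 26, critical t 2.048 to 2.056), and power goes from about 75.3% to 75.1%.
- **Ordinary chance imbalance, covariates irrelevant:** about 72%. The extra loss comes from the chance imbalance, not from the degrees of freedom.
- **A real age gap of 1 SD:** about 62-66%, with standard errors 12-17% larger.
- **A real age gap of 2 SD:** about 43-46%, with standard errors 44-51% larger.

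The last two ranges cover age correlations from 0 to 0.3. At a wide gap the adjusted estimate also leans on a linear age effect across weakly overlapping groups and should be read with caution, which is a further reason to show both estimates.
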